5.1 The Scientific Question of Interest

The scientific question of interest evaluates the potential superiority of TTP399 over placebo in the treatment of T1DM in patients who meet protocol eligibility criteria and do not require concomitant medications, blood transfusions, or other rescue therapies that would influence HbA1c measures (except for insulin), thereby rendering the subsequent values as uninterpretable for protocol-planned purposes.

5.2 The Population of Interest

The population of interest includes qualified patients who meet eligibility criteria specified in the protocol who do not require concomitant medications that would taint HbA1c measures for protocol purposes (except for insulin) or have blood transfusions and who complete 12 weeks of treatment with TTP399 or placebo.

5.3 The Variable of Interest

The endpoint or variable of primary interest is change in HbA1c. Additionally, a responder analysis is of keen interest, where a responder is a subject who shows stable or improved HbA1c at endpoint (change is zero or more), no treatment-emergent abnormal value in beta-hydroxybutyrate (BOHB), and no increase in hypoglycemic episodes below 54 mg/ml. Of key interest are parameters associated with glycemic control, including percentage of time in the target range and the coefficient of variation (CV). Important variables of interest from a safety perspective include time in hypoglycemic ranges and occurrence of adverse events of special interest, including severe hypoglycemia and DKA.

5.4 The Specification of How Intercurrent Events Are Reflected in the Scientific Question of Interest

An intercurrent event is any event that occurs after treatment initiation and either precludes observation of the variable or affects its interpretation (ICH E9 addendum, glossary).

Intercurrent events for Part 2 of this study include:

- Blood transfusion.
- Use of concomitant treatments that are known to be associated with impact on HbA1c, specifically use of steroids.
- Shift change in work schedule from day worker to night worker or other life event that may affect HbA1c, such as any situation or major protocol deviation from the usual insulin doses outside of the ones specified in the protocol.

Data from patients during periods of when the InPen or insulin pump fails cannot be interpreted for the protocol-planned purposes. Censored data will invoke statistical methodologies for coping with missingness.

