Noninferiority will be considered to have been established if the 95% confidence interval is completely bounded by the non-inferiority margin of 0.3%, which is specified in the draft guidance: *Guidance for Industry Diabetes Mellitus: Developing Drugs and Therapeutics Biologics for Treatment and Prevention* (CDER; February 2008), Section V.G.1, “Typically we accept a noninferiority margin of 0.3 or 0.4 HbA1c percentage units provided this is no greater than a suitably conservative

estimate of the magnitude of the treatment effect of the active control in previous placebo-controlled trials.”

- The 95% confidence interval will be constructed for the difference between the two treatment groups in mean change in HbA1c to Week 12 using the ANCOVA model as described in the statistical methodology section.
- If the 95% confidence interval is entirely bounded by 0.3% (where a difference of 0.3% reflects the placebo mean is 0.3% better than the mean of the patients treated with TTP399), then the statistical conclusion will follow that treatment with 800 mg TTP399 combined with a modified regimen of insulin is non-inferior to placebo added to insulin following the usual standard of care.

Conditional on the statistical conclusion of non-inferiority of TTP399 relative to placebo, statistical evaluation continued.

It is noted that noninferiority relative to change from baseline in insulin is planned using the confidence interval approach to demonstrate that the maintenance of control of HbA1c achieved during the insulin-optimization period is not driven by an increase in insulin among subjects treated with TTP399. Formal evaluation of this aspect of non-inferiority is not planned, so the statistical evaluation is considered to be nominal rather than rigorous.

The Hochberg method is used for alpha control for Evaluation 2 and Evaluation 3.

- **Evaluation 2:**

Superiority on HbA1c is evaluated:

- H_{01} : The change from baseline in HbA1c at Week 12 for the group treated with 800 mg TTP399 is equal to that of the placebo group.
- H_{11} : The change from baseline in HbA1c at Week 12 for the group treated with 800 mg TTP399 is not equal to that of the placebo group.

- **Evaluation 3:**

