It is noted that strict application of the Hochberg methodology implies that rigorous p-values may not be applicable in the event of failure to reject either hypothesis in Evaluation 2. The intersection hypothesis is, however, applicable, and it is the intention of this analysis plan to continue testing under the intersection hypothesis and interpret p-values as rigorous as opposed to nominal.

Superiority on treatment response is evaluated:

- H_{02} : The proportion of treatment responders at Week 12 for the group treated with 800 mg TTP399 is equal to that of the placebo group.
- H_{12} : The proportion of treatment responders at Week 12 for the group treated with 800 mg TTP399 is not equal to that of the placebo group.

The study is declared to have met its primary endpoint if Evaluation 1 concludes TTP399 plus the modified regimen of insulin is noninferior to optimized insulin

And

Using the Hochberg method, either Evaluation 2 finds TTP399 is superior on HbA1c or Evaluation 3 finds TTP399 is superior on the proportion of treatment responders.

Conditional on achievement of endpoints, statistical evaluation continues.

Conditional Second Statistical Evaluation:

- **Evaluation 4:**

Superiority on daytime time in range is evaluated:

- H_{03} : The mean change in daytime time in range from baseline to Week 12 for the group treated with 800 mg TTP399 is equal to that of the placebo group.
- H_{13} : The mean change in daytime time in range from baseline to Week 12 for the group treated with 800 mg TTP399 is not equal to that of the placebo group.

Conditional Third Statistical Evaluation:

- **Evaluation 5:**

Superiority on time in hypoglycemia using 70 mg/dl as the threshold is evaluated:

- H_{04} : The mean change in time in hypoglycemia using 70 mg/dl as the threshold from baseline to Week 12 for the group treated with 800 mg TTP399 is equal to that of the placebo group.
- H_{14} : The mean change in time in hypoglycemia using 70 mg/dl as the threshold from baseline to Week 12 for the group treated with 800 mg TTP399 is not equal to that of the placebo group.

Conditional Fourth Statistical Evaluation:

- **Evaluation 6:**

Superiority on time in hypoglycemia using 54 mg/dl as the threshold is evaluated:

- H_{05} : The mean change in time in hypoglycemia using 54 mg/dl as the threshold from baseline to Week 12 for the group treated with 800 mg TTP399 is equal to that of the placebo group.

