6.1 Efficacy Variables

6.1.1 Primary Efficacy

The primary efficacy variables of analysis include the following:

- Change from baseline to Week 12 in HbA1c.
- Proportion of Responders, where a responder meets the following criteria:
 - HbA1c: has a change in HbA1c of less than zero (any improvement)
 - Ketoacidosis: has no treatment-emergent serum BOHB above the normal reference range
 - Lactic acidosis: has no treatment-emergent lactic acid above the normal reference range.
 - Hypoglycemia: has no treatment-emergent episode of severe hypoglycemia (related or not related).

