6.1.2 Secondary Efficacy

Secondary variables of analysis include:

- Achievement of no more than trace ketones in urine post-treatment
- Achievement of no treatment-emergent abnormal value in serum BOHB
- Achievement of no more than trace ketones in urine or treatment-emergent abnormal value in BOHB in serum
- Change from baseline relative to:
 - Time in target glycemic range (70-180 mg/dL);
 - Time in hyperglycemic range
 - Level 1 > 180 mg/dL
 - Level 2 > 250mg/dL
 - Time in hypoglycemic range
 - Level 1 < 70mg/dL
 - Level 2 < 54 mg/dL
- Change from baseline in average daily number of units of bolus insulin dose
- Percent change from baseline in average daily insulin dose
- Achievement of a decrease of at least 0.3% in HbA1c at Week 12 (responders)

Additionally, analysis will be done on hypoglycemia both thresholds (54 mg/dl and 70 mg/dl) using the following variables:

- Change from baseline (2-week period) to Week 12 (2-week period) on the number of hypoglycemia episodes
- Proportion of patients with at least one more treatment-emergent episode of hypoglycemia at Week 12 (2-week period) relative to baseline (2-week period).
- Time-adjusted change from baseline on the number of hypoglycemia episodes.
- Proportion of patients with at least one more time-adjusted treatment-emergent episode of hypoglycemia at Week 12 than at baseline.

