7.6.3 Continuous Glucose Monitoring

Continuous glucose monitoring (CGM) data will be analyzed with the following categories of interest:

- Level 2 hypoglycemia: < 54 mg/dl
- Level 1 hypoglycemia: < 70 mg/dl
- Normal or target: in the range 70-180 mg/dl
- Level 1 hyperglycemia: > 180 mg/dl
- Level 2 hyperglycemia: > 250 mg/dl

Supportive analysis will be done on the endpoint percentages of subjects in the target range or outside of the range by level.

Additionally, non-overlapping categories will be examined:

- Level 2 hypoglycemia: < 54 mg/dl
- Level 1 hypoglycemia: between 54 (inclusive) and 70 (not inclusive) mg/dl
- Normal or target: in the range 70-180 mg/dl
- Level 1 hyperglycemia: > between 180 (not inclusive) and 250 (inclusive) mg/dl
- Level 2 hyperglycemia: > 250 mg/dl

Average daily glucose at endpoint and change in average daily glucose will also be done as supportive analysis. The comprehensive analysis will also include standard deviation and CV.

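### SAP 5.3 reverses the sign of the HbA1c responder criterion and gives the hypoglycemia threshold in mg/ml; both errors reach Evaluation 3 only if 5.3, rather than 6.1.1, is the definition programmed

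*SAP*

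**What the plan says.** SAP 5.3 lies within the specification of the estimand. It states that "a responder is a subject who shows stable or improved HbA1c at endpoint (change is zero or more", and further requires no treatment-emergent abnormal beta-hydroxybutyrate (BOHB) and "no increase in hypoglycemic episodes below 54 mg/ml".

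SAP 6.1.1 lists the responder criteria again, among the primary efficacy variables. There the patient "has a change in HbA1c of less than zero (any improvement", has no treatment-emergent BOHB or lactic acid above the reference range, and meets a different safety condition: "Hypoglycemia: has no treatment-emergent episode of severe hypoglycemia (related or not related".

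SAP Section 2 tests the responder proportion as Evaluation 3. It speaks only of treatment responders and cites neither 5.3 nor 6.1.1. After non-inferiority is shown (Evaluation 1), the primary endpoint is met if either Evaluation 2 (mean HbA1c change) or Evaluation 3 shows superiority, with Hochberg control across the two. SAP Section 3 gives the responder variable co-primary importance, and 5.5 takes the placebo-subtracted proportion of responders as its summary measure.

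**The concern.** Two thresholds in 5.3 are misstated.

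- **Sign.** The parenthesis is meant to explain the words just before it. With change taken as Week 12 minus baseline, zero or more means stable or worse, which contradicts those words.
- **Unit.** The threshold is given per millilitre, whereas the SAP's CGM categories and hypoglycemia endpoints are given per decilitre.

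This is the rule for counting a success on a primary variable, placed in the estimand section, so it is more than background text. A programmer who coded 5.3 literally would count the patients whose HbA1c did not fall and would lose the hypoglycemia safeguard. The SAP gives no order of precedence between 5.3 and 6.1.1, so nothing on the page prevents that choice.

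**Working it through.** **1. Sign convention.** Two other places in the SAP fix it. In 6.1.1 improvement is a change below zero. In Section 2 the non-inferiority rule is explained as "where a difference of 0.3% reflects the placebo mean is 0.3% better than the mean of the patients treated with TTP399", so a positive difference means that TTP399 did worse and a lower change is better. Under this convention stable or improved is change ≤ 0, and the parenthesis in 5.3 (change ≥ 0) agrees with it only at exactly zero.

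**2. Unit.** The plan's own figure first: Protocol 9.8.2 equates 54 mg/dl with 3.0 mmol/l. With a molar mass of glucose of 180.16, 54 × 10 / 180.16 = 2.997 mmol/l, which reproduces it. As written in 5.3:

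- 54 mg/ml × 100 ml/dl = 5400 mg/dl, or 5400 × 10 / 180.16 = 299.7 mmol/l.
- 5400 / 54 = 100 times the intended level.
- 5400 / 400 = 13.5 times the 400 mg/dl above which SAP 8.2 calls for blinded review.

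The intended unit is clear from the rest of the SAP: "Level 2 hypoglycemia: < 54 mg/dl" in 7.6.3, "analysis will be done on hypoglycemia both thresholds (54 mg/dl and 70 mg/dl" in 6.1.2, and 54 mg/dl in Evaluation 6. Every plausible reading lies below 5400 mg/dl, so the criterion cannot separate level 2 hypoglycemia from any other glucose value.

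**3. The two definitions side by side.**

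| | SAP 5.3 | SAP 6.1.1 |
|---|---|---|
| HbA1c | stable counts (sign reversed as written) | any decrease required |
| BOHB | no treatment-emergent abnormal value | none above the reference range |
| Lactic acid | not mentioned | none above the reference range |
| Hypoglycemia | no increase in episodes below 54 (unit wrong) | no severe episode |

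Correcting the sign and unit leaves the HbA1c, lactic acid and hypoglycemia rows different.

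**4. Illustration if 5.3 were programmed literally.** Inputs from the SAP: effect 0.7%, SD 1%, alpha 0.049 (1.9 and Section 7), 45 per arm (Table 1). Assumptions: normally distributed change, placebo mean change 0 (the documents give none; range −0.3 to +0.3), all other responder criteria ignored.

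- Literal rule: P(change ≥ 0) = 1 − Φ(0.7) = 0.242 on TTP399 and 1 − Φ(0) = 0.500 on placebo, a difference of −25.8 points (−22.3 to −27.3 over the range).
- Corrected sign: 0.758 against 0.500, or +25.8 points.
- Exact enumeration of Fisher's test at 0.049 under the literal rule: significantly favours placebo with probability 0.645 (0.59 to 0.66 over the range), and TTP399 with probability about 9 × 10⁻⁷. With the corrected sign, power for TTP399 is 0.645.
- At 0.0245, the Hochberg level when the other test fails, 0.645 becomes 0.535.
- With placebo change 0, effects of 0.3% to 0.7% and SDs of 0.6% to 1.0%, the literal TTP399 rate runs from 1 − Φ(0.7/0.6) = 12% to 1 − Φ(0.3/1.0) = 38%, below the placebo 50% throughout.

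**5. The other superiority route.** Evaluation 2 does not use the responder rule. At 0.7%, SD 1% and 45 per arm, an unadjusted t-test has about 85% power even at 0.0245.

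**The case against.** The strongest reply is that the errors need never reach the analysis. SAP 6.1.1 sets out the responder criteria item by item under the primary efficacy variables, with the right sign and no 54 threshold. If it governs, both slips in 5.3 are harmless. The intent is also easy to recover: the words before the parenthesis are right, a reader could take change to mean the size of the improvement, and mg/dl appears throughout. All of this stands, and it limits the consequence. It does not remove the point, because the SAP never says that 6.1.1 overrides 5.3, and 5.3 does not define change as baseline minus endpoint.

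The illustration is also not the plan's full Evaluation 3. It leaves out the other criteria. It uses Fisher's test, which 7.6 names, whereas 7.6.1 names logistic regression with baseline covariates. It shows direction and rough size, no more.

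A reader might infer two stronger things that the documents do not support.

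- **That the trial's conclusion would be reversed.** The responder test is one of two superiority routes after non-inferiority. Evaluation 2 is untouched, and the literal rule would almost never produce a false success.
- **That the hypoglycemia criterion would be met by nearly every patient.** It counts episodes, not readings. Under the event rule in Protocol 9.8.2, an episode ends after 15 minutes at or above 70 mg/dl. With a 5400 mg/dl threshold the start and end conditions can hold together, so the count would mainly follow wear time and time at or above 70 mg/dl, and it could rise between periods. Only the weaker statement is safe: the criterion says nothing about level 2 hypoglycemia.

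**Conclusion.** The point holds as a drafting error in a decision rule. In SAP 5.3 the HbA1c parenthesis has the wrong sign under the SAP's own convention, and the hypoglycemia threshold is 100 times too high. Whether this affects Evaluation 3 depends on which section is programmed, and the SAP leaves that open. If it is 5.3 taken literally, the expected responder difference on the HbA1c component turns from about +26 to about −26 points. The responder test would then significantly favour placebo roughly 64% of the time at 0.049 and 53% at 0.0245, under the assumptions in the working. If it is 6.1.1, there is no effect on the analysis.

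The larger open matter is that two responder definitions coexist. The 49-per-group calculation in SAP 1.9 does not settle it: it concerns a fall of at least 0.3%, which is neither composite. The correction changes no sample size or alpha figure.

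**What to change.** Before unblinding, delete the responder criteria from SAP 5.3 and refer there, and in Evaluation 3, to the single responder definition that is retained.

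If the 5.3 criteria are kept instead, replace the parenthesis with Week 12 minus baseline HbA1c is zero or less, replace mg/ml with mg/dl, and make 6.1.1 match on stable HbA1c, lactic acid and the type of hypoglycemia event.

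The cost is a short SAP amendment. No new data are needed.

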5.5 The Population-Level Summary for the Variable

The mean change in HbA1c is of primary interest supported by the mean endpoint value of HbA1c to be used to compare patients treated with TTP399 with those treated with placebo. The placebo-subtracted proportion of responders is the population-level variable of interest for the responder analysis.

6 Variables of Analysis

6.1 Efficacy Variables

6.1.1 Primary Efficacy

The primary efficacy variables of analysis include the following:

- Change from baseline to Week 12 in HbA1c.
- Proportion of Responders, where a responder meets the following criteria:
 - HbA1c: has a change in HbA1c of less than zero (any improvement)
 - Ketoacidosis: has no treatment-emergent serum BOHB above the normal reference range
 - Lactic acidosis: has no treatment-emergent lactic acid above the normal reference range.
 - Hypoglycemia: has no treatment-emergent episode of severe hypoglycemia (related or not related).

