9.8.3. Management of Diabetic Ketoacidosis

Typical symptoms of diabetic ketoacidosis (DKA) are thirst or a very dry mouth, frequent urination, high blood glucose (blood sugar) levels, or high levels of ketones in the urine. DKA is an AE of special concern in this population and should be described to the patients. Home monitoring should be undertaken in the event patients experience blood glucose ≥ 240 mg/dL during an illness or in the presence of symptoms described above. Patients should call the study site if they measure moderate or high ketone values.

Diabetic Ketoacidosis (DKA) is defined by

- c) Increased serum β - hydroxybutyrate or urine ketones (above ULN)
AND
- d) serum bicarbonate (total CO_2) < 15 mmol/L **OR** blood pH < 7.3

Episodes of diabetic ketoacidosis will be adjudicated by an independent data monitor in Part 1 and Part 2.

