- H_{15} : The mean change in time in hypoglycemia using 54 mg/dl as the threshold from baseline to Week 12 for the group treated with 800 mg TTP399 is not equal to that of the placebo group.

Conditional Fourth Statistical Evaluation:

- **Evaluation 7:**

Superiority on Quality of life Likert scale score is evaluated:

- H_{06} : The mean score for the single-item Likert scale for overall improvement in quality of life at Week 12 for the group treated with 800 mg TTP399 is equal to that of the placebo group.
- H_{16} : The mean score for the single-item Likert scale for overall improvement in quality of life at Week 12 for the group treated with 800 mg TTP399 is not equal to that of the placebo group.

3 Estimand Specification

This SAP is constructed to conform to regulatory guidance. In particular, this section is included as recommended by ICH E9 (R1) Addendum on estimands and sensitivity analysis in clinical trials to the guideline on statistical principles for clinical trials (30 August 2017).

In accordance with ICH E9 Addendum, the specification of the estimand is included in this SAP with the 4 attributes detailed in ICH E9 Addendum, Section A.3.1:

A. The Population, that is, the patients targeted by the scientific question:

For this study, the population consists of subjects with type 1 diabetes who meet eligibility requirements for the study, have qualified through the basal insulin-optimization period (if needed) and the placebo run-in period, receive double-blind medication, and have at least one valid post-baseline measure of HbA1c.

B. The variable (or endpoint) to be obtained for each patient, that is required to address the scientific question:

For this study, the primary endpoint is HbA1c with co-primary importance on treatment responsiveness (whether or not subjects are treatment responders).

C. The specification of how to account for intercurrent events to reflect the scientific question of interest:

For this study, intercurrent events such as blood transfusion or medical treatment with prednisone or major modification in insulin regimen/doses outside the once recommended in the protocol that would render subsequent values as not protocol-meaningful will be set to missing (moved to the SDTM SUPPLB domain to facilitate sensitivity analysis that includes the values) and primary statistical methodologies of multiple imputation will be used to predict what the values were likely to be had the intercurrent event not happened.

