6.1.3 Tertiary and Exploratory Efficacy

- Standard deviation of daily CGM and associated CV%
- Plasma (non-genomic) biomarkers
- Diabetes treatment satisfaction questionnaire (s)
- Change from baseline in number of bolus injections of insulin
- An analysis of responders HbA1c < 7% without any severe hypoglycemic events, weight gain, diabetic ketoacidosis

Additionally, a quality of life (Likert Scale) question is classified as an exploratory variable of interest: At Week 12, the patient should be asked to respond to the following QOL question with one of the answers below. The answer will be entered in the EDC.

Question: “How is your quality of life relative to study start?”

Answers (choose one): markedly worse, moderately worse, slightly worse, no change, slightly improved, moderately improved, markedly improved.

The Diabetes Treatment Satisfaction Questionnaire status version (DTSQs) is completed at Screening and Week 12, and the Diabetes Treatment Satisfaction Questionnaire change version (DTSQc) is completed at the Week 12 visit. These questionnaires will be evaluated as exploratory variables of analysis in this Part.

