6.2.3 Clinical laboratory assessments

Clinical laboratory variables of analysis include raw means and mean changes from baseline for the clinical laboratory measures in this study

- Hematology: hemoglobin, hematocrit, RBC count, platelet count, WBC count, total neutrophils (abs), eosinophils (abs), monocytes (abs), basophils (abs), lymphocytes (abs)
- Clinical chemistry: BUN, creatinine, calcium (total), sodium, potassium, chloride, total carbon dioxide, (bicarbonate), AST (SGOT), ALT (SGPT), alkaline phosphatase (ALK), total bilirubin, direct (conjugated) bilirubin, uric acid, albumin, total protein
- Lipid panel: total cholesterol, HDL-C, LDL-C, triglycerides
- Specialty laboratory tests: HbA1c, C-peptide, lactate, ketones, free fatty acids, GGT, fructosamine, glucagon, 1, 5 anhydroglucitrol.

A treatment-emergent abnormal value (TEAV) is a laboratory analyte that is abnormal after administration of study medication that was not present prior to the administration of study medication.

Safety variables of analysis include:

- Proportions of patients with TEAVs
- Proportions of patients with a TEAV in any liver function test (LFT) including ALT, AST, total bilirubin, alkaline phosphatase.

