7.7.4 Clinical Laboratory Measurements

Because “exacerbations” of pre-existing abnormalities in laboratory analytes are examined using clinical judgment and are reported as TEAEs, additional analysis on TEAVs is limited to subjects with values that are normal prior to dosing and abnormal after dosing.

Adverse events of special interest also treatment-emergent abnormal values (TEAVs) in laboratory parameters related to liver function tests, specifically ALT, AST, bilirubin, and ALK.

Potentially clinically significant values in laboratory analytes will be examined in accordance with the table of values or changes of potential clinical significance in this SAP. Proportions of subjects in each treatment group who meet the criteria will be analyzed.

Laboratory data will be summarized by Baseline and change from Baseline to each scheduled assessment time with descriptive statistics.

Liver function tests have additional monitoring for this study.

To explore the potential for drug-induced liver injury consistent with *Guidance for Industry “Drug-induced liver injury: premarketing clinical evaluation”* (CDER, CBER, July 2009), subjects will be summarized and listed who meet the following criteria:

- (1) Elevations in either AST or ALT of at least 3-times the upper limit of normal, and

- (2) An accompanying abnormal bilirubin.

Additionally, a summary and listing will be examined for subjects with elevations in either AST or ALT of at least 3-times the upper limit of normal, regardless of bilirubin.

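### The 'Ketoacidosis' component of the co-primary responder tests only treatment-emergent serum BOHB, so some patients with an adjudicated DKA would pass it

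*SAP*

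**What the plan says.** SAP 6.1.1 defines a responder by four criteria: a fall in HbA1c, a ketone criterion, a lactate criterion and a hypoglycemia criterion. The ketone criterion is "Ketoacidosis: has no treatment-emergent serum BOHB above the normal reference range". The hypoglycemia criterion, by contrast, uses a clinical event, severe hypoglycemia. SAP 5.3 describes a somewhat different responder, but its ketone condition is again only a treatment-emergent abnormal BOHB.

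For laboratory values, SAP 6.2.3 gives this meaning: "A treatment-emergent abnormal value (TEAV) is a laboratory analyte that is abnormal after administration of study medication that was not present prior" to dosing. SAP 7.7.4 says that analysis of such values is "limited to subjects with values that are normal prior to dosing and abnormal after dosing"; worsening of an existing abnormality is left to adverse-event reporting.

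Protocol 9.8.3 defines DKA differently. The ketone limb is met by raised serum beta-"hydroxybutyrate or urine ketones (above ULN"), and it must be joined by serum bicarbonate below 15 mmol/L or blood pH below 7.3. The same section states: "Episodes of diabetic ketoacidosis will be adjudicated by an independent data monitor in Part 1" and also in Part 2.

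On the weight of the responder, SAP Section 3 states: "For this study, the primary endpoint is HbA1c with co-primary importance on treatment responsiveness". SAP Section 2 declares the primary endpoint met if non-inferiority is shown and, under the Hochberg method, either HbA1c superiority is shown or "Evaluation 3 finds TTP399 is superior on the proportion of treatment responders".

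**The concern.** The criterion carries the name of a clinical event but is decided by one analyte, and only by a change in that analyte from normal to abnormal. The trial has a defined and adjudicated version of that event, and the responder rule does not use it. The exploratory responder in SAP 6.1.3 does: "An analysis of responders HbA1c < 7% without any severe hypoglycemic events, weight gain, diabetic ketoacidosis".

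At stake is what a positive responder result would mean. SAP 7.6.6 presents protection from ketoacidosis as a possible advantage of TTP399, so readers will take this component literally. If a patient who had a DKA can be scored as a success, the claim does not say what its label says.

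**Working it through.** **1. The plan's own responder figure.** SAP 1.9 and protocol 10.2 give 49 per group for 30% versus 60%, 80% power and alpha 0.049. With mean rate 0.45 and difference 0.30, n = [1.969 × √(2 × 0.45 × 0.55) + 0.842 × √(0.30 × 0.70 + 0.60 × 0.40)]² / 0.30² ≈ 42.2, which rounds up to 43. The continuity correction, (n/4) × [1 + √(1 + 4/(0.30n))]², gives about 48.7, so 49. The figure reproduces, but it belongs to a responder defined by an HbA1c fall of at least 0.3%. No rate is given for the four-part responder, so the figure does not bear on this point.

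**2. Which baseline counts.** In Part 2, protocol Appendix 2 schedules BOHB at Week 0, Week 2, Week 6, Week 12/ET and Follow-up, and not at Screening. There is therefore one scheduled pre-dose value, and it decides whether a patient is normal before dosing. SAP 7.1 keeps Follow-up data out of the efficacy analysis, which leaves Weeks 2, 6 and 12/ET as the scheduled on-treatment samples.

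**3. Applying the rule.** The component fails only if BOHB was normal before dosing and a high serum value is recorded afterwards.

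| Day 1 BOHB | High post-dose serum BOHB on record | DKA | Component as written |
|---|---|---|---|
| Normal | No | No | Pass |
| Normal | No | Yes | **Pass** |
| Normal | Yes | No | Fail |
| Normal | Yes | Yes | Fail |
| High | No | No | Pass |
| High | No | Yes | **Pass** |
| High | Yes | No | Pass |
| High | Yes | Yes | **Pass** |

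Three of the four DKA rows pass. These are logical cases, not frequencies. The second row can arise because urine ketones alone satisfy the ketone limb of the DKA definition, or because the episode was treated elsewhere between visits.

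**4. Number exempt through a high Day 1 value.** The share is not given. Assume that 5% to 30% of the 45 patients per arm have a high Day 1 BOHB, and that 25% to 75% of those are high again on treatment. Then 45 × 0.05 × 0.25 ≈ 0.6 to 45 × 0.30 × 0.75 ≈ 10.1 patients per arm would pass despite a repeat high value. These are repeat elevations, not DKA cases, and randomization should spread them over both arms.

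**5. Sensitivity of the test.** If Evaluation 3 has to succeed alone, the usual Hochberg rule requires p ≤ 0.049/2 = 0.0245. With assumed counts of 27/45 versus 14/45, Fisher's p is 0.011. Reclassifying TTP399 responders one at a time gives 0.019, 0.033 and 0.054. With these counts, the second reclassification crosses 0.0245 and the third crosses 0.049. This shows only that small counts can matter at this sample size. The counts are invented, and they change one arm only.

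**The case against.** - **Most DKA would already fail.** With a normal Day 1 value, any post-dose BOHB above range fails the patient, a much lower bar than DKA. This stands for every normal-baseline patient with a high serum value on record. SAP 6.1.1 does not restrict itself to scheduled samples, and SAP 8.10 admits unscheduled values to maximum-over-time summaries. But no rule says that those, or local hospital values, feed the responder.
- **SAP 7.7.4 is a safety rule that 6.1.1 does not cite.** True; the reading is inferred. It is still the natural one: 6.2.3 gives the same meaning, and 5.3 and 6.1.2 both treat BOHB as a treatment-emergent abnormal value. The wording that includes exacerbation (SAP 6.2.1) is for adverse events. If exacerbation was meant here, the SAP should say so.
- **DKA is reported anyway.** It is an adverse event of special interest (SAP 7.7.1), and non-responder imputation (SAP 7.5) covers a patient who leaves with the endpoint missing. Neither changes the status of a patient who has a DKA and also has a Week 12 HbA1c.
- **Events will be rare.** Probably so: protocol 5.3.2 excludes DKA within the last year, and protocol 3.4.1 reports none in the five sentinel patients.

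A reader might go further and infer that a patient with high Day 1 BOHB becomes a responder automatically, or that any DKA patient can be one. The documents do not support either. The exemption covers one criterion of four, and a DKA with a normal baseline and a recorded high serum BOHB fails. A reader might also take the label itself as an error, because a slight BOHB rise fails a patient under the name of ketoacidosis. That is a matter of preference: the neighbouring lactic acidosis line is built the same way, and the documents give no basis for saying how often it would happen.

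**Conclusion.** The point holds as a gap in the definition of a co-primary endpoint. As written, this component passes a patient with Day 1 BOHB above range whatever happens later, and a patient with a normal baseline whose DKA left no high serum BOHB on record. If that patient also meets the HbA1c, lactate and hypoglycemia criteria, a DKA is scored as a success.

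The conclusion rests on reading the ketone criterion through SAP 6.2.3 and 7.7.4, since 6.1.1 gives no definition of its own. Its size cannot be estimated: the documents state neither the share with high Day 1 BOHB nor an expected number of DKA events, and few misclassified patients are likely. It deserves correction because Evaluation 3 can carry the primary claim once non-inferiority is shown, and because the remedy uses an event the trial already adjudicates.

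**What to change.** Before unblinding, add to the responder definition in SAP 6.1.1 and 5.3: *no adjudicated DKA event (protocol 9.8.3) after the first double-blind dose, regardless of baseline BOHB*. State where that window closes, given that SAP 7.1 keeps Follow-up data out of efficacy.

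Also state how the BOHB line applies when the Day 1 value is abnormal, and whether unscheduled or local values count. Requiring later values to stay at or below the patient's own baseline is one option, but a single Day 1 reading is a noisy threshold, so this part is open to choice. Renaming the line 'ketonemia' is optional.

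The cost is a few lines of SAP text and a small change to the derivation. No new data collection is needed, because adjudication is already planned. The downside is that the responder rate may fall slightly.
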